	Assigning Relationship of Adverse Events to Treatment.....	48
	Serious Adverse Events	49
	Definition of a Serious Adverse Event.....	49
	SAE report to Sponsor and IRB	50
5.0	STATISTICAL AND ANALYTICAL PLAN	51
	Intent to Treat Population	51
	Safety Population	51
	Evaluable Population	51
	Missing Data	52
	Assessment of Safety	53
6.0	REGULATORY AND ADMINISTRATIVE REQUIREMENTS.....	53
6.1	IRB Requirements.....	53
6.2	Protocol Amendments	54
6.3	Informed Consent.....	55
APPENDIX I:	QUESTIONNAIRES/SURVEYS	56

PROTOCOL SYNOPSIS

Protocol Number	1015456
Title	A STUDY TO DETERMINE EFFICACY OF EASY GRAFT CLASSIC FOR THE TREATMENT OF PERI-IMPLANTITIS
Subject Population	Subjects with history of Moderate to Severe Peri-implantitis
Objectives	TO ASSESS THE EFFECTIVENESS OF EFFICACY OF EASY GRAFT CLASSIC
Number of Subjects	Maximum of 15 subjects
Number of Sites	Maximum 20 implants
Safety Endpoints	Assessments of subject safety will be based upon tabulations of the incidence of adverse events.
Efficacy Endpoints	
Stability and health of the attachment apparatus at 6 and 12 months by measuring:
 
 • Change from baseline in probing depth • Change from baseline in clinical attachment level • Change from baseline in width of the keratinized tissue • Change from baseline in radiographic A) bone regeneration ; B) pathology • Esthetic satisfaction from baseline to 12 months, as assessed by both the examiner and the subject using the Visual Analog Scale (VAS), prior to and after viewing baseline photos • Subject pain/discomfort questionnaire

CONFIDENTIAL AND PROPRIETARY INFORMATION OF Creighton University School of Dentistry Department of Periodontics

Protocol Number: CUSD2

Revision: October 22nd 2018

Original Issue Date: January 6th 2017

	
This study will be “case series”. Two periodontists will perform surgical procedures and record surgical measurements. The blinded examiner will perform all other clinical assessments. 15 subjects will be enrolled. Written informed consent will be obtained from each subject prior to any study related procedures. The study will follow subjects for safety and efficacy for 12 months after their surgical treatment.
 
Study Design
 
The day of surgery will be designated as Day 0. Subjects will have a guided bone regeneration surgery with GUIDOR® easy-graft® CLASSIC and GUIDOR® Bioabsorbable Membrane Matrix for the implants experiencing peri-implantitis. The surgical side will be assessed for osseous and implant surface anomalies. Intraoperative and postoperative measurements will be made and the flap will be closed with sutures.

--	---

1.0 BACKGROUND

Peri-implantitis is an infectious condition of the tissues around dental implants causing loss of supporting bone and clinical signs of inflammation such as bleeding and/or suppuration on probing). The prevalence of this disease regards almost 10% of implants and almost 20% of

patients^{1,2}. Many factors influence and increase prevalence (and the risk) of peri-implantitis.

Some of those are previous history of periodontitis, smoking, diabetes as well as the type and frequency of follow-up care. It is worth noting that the prevalence of peri-implantitis varies depending on the parameters used in scientific papers. Bone loss and/or probing depth threshold may vary among different authors modifying the case definition.

Different clinical protocols for treatment of peri-implantitis have been proposed, including mechanical debridement, the use of antiseptics and local or systemic antibiotics, as well as surgical access and regenerative procedures. Several attempts to combine the data of the available literature in a meta-analysis have failed in the past due to insufficient data.^{3,4,5,6,7,8}

Mombelli et al, in their review⁹ noted that almost all studies on the treatment of peri-implantitis in humans do not satisfy the strict criteria for a randomized controlled trial (RCT).

The main limitation was the absence of a true control group (no treatment or placebo). Trials at the highest level of evidence compared test procedures, both of which had an unclear

¹ Mombelli A, Müller N, Cionca N. The epidemiology of periimplantitis. *Clin Oral Implants Res* 2012;23(suppl 6):67–76.

² Lee CT, Huang YW, Zhu L, Weltman R. Prevalences of peri-implantitis and peri-implant mucositis: systematic review and meta-analysis. *J Dent*. 2017 Jul;62:1-12. doi: 10.1016/j.jdent.2017.04.011. Epub 2017 May 3. Review.

³ Klinge B, Gustafsson A, Berglundh T. A systematic review of the effect of anti-infective therapy in the treatment of peri-implantitis. *J Clin Periodontol* 2002;29(suppl 3):213–225; discussion 232–213.

⁵ Renvert S, Roos-Jansaker AM, Claffey N. Non-surgical treatment of peri-implant mucositis and peri-implantitis: A literature review. *J Clin Periodontol* 2008;35:305–315.

⁶ Renvert S, Polyzois I, Claffey N. Surgical therapy for the control of peri-implantitis. *Clin Oral Implants Res* 2012;23(suppl 6):84–94.

Daugela et al¹² reported that in case of evident bone loss and pocket formation deeper than 5 mm, the surgical treatment seemed to be the only effective one in managing peri-implantitis defect. Surgical regenerative treatment resulted in predictable improvement of peri-implant clinical and radiographic parameters although this statement is limited on available studies without proper control arm, as at the time there is a lack of controlled studies comparing effectiveness of surgical regenerative and non-regenerative procedures to support scientific evidence if regenerative procedures provide better outcomes.

Currently there is a lack of clear recommendation regarding choice of biomaterials for peri-implant bone regeneration due to high heterogeneity among the studies. From the clinical point of view, surgical regenerative treatment is a relevant treatment option of intrabony defect component in addition to pre- and postsurgical hygiene maintenance phases and successful implant surface decontamination. Regenerative procedures, with the application of bone graft materials in combination or not with barrier membranes seem to give consistent results in the term of hard and soft tissues healing of the peri-implantitis defect.

Regenerative treatment of peri-implantitis lesions can be performed in cases with considerable pocket formation and bone loss after the acute infection has been resolved and proper oral hygiene has been instituted. Reported clinical studies indicate that considerable bone regeneration and re-osseointegration can be obtained by using various types of bone graft materials and membranes. Meta-analysis of latest systematic literature review ^{xi} revealed that

¹²Daugela P, et alSurgical Regenerative Treatments for Peri-Implantitis: Meta-analysis of Recent Findings in a Systematic Literature Review. J CONFIDENTIAL AND PROPRIETARY INFORMATION OF Creighton University School of Dentistry Department of Periodontics
Protocol Number: CUSD2
Revision: October 22nd 2018
Original Issue Date: January 6th 2017

the weighted mean of marginal bone level change was 1.97 mm, PD reduction was 2.78 mm and BOP reduced by 52.5% by treatment with regenerative treatment. However, a different compatibility between bone grafting material and chemically and mechanically decontaminated implant surface might bring a different clinical outcome.

As far as the use of alloplastic grafting material, only two papers were identified in the literature. Roos-Jansåker et al.^{13, 14} evaluated regenerative treatment of peri-implantitis comparing a bone substitute with or without a barrier membrane. Peri-implant defects were treated with a phytogenic calcium carbonate bone substitute (Algipore) or with the bone substitute and a resorbable synthetic membrane (Osseoquest). Successful treatment outcome (no PD ≤ 5 and no further bone loss 12mo after treatment) was on 93% of patient treatment with bone substitute and membrane and 89% of patients treated with bone substitute only.

Schwarz et al¹⁵ filled peri-implant defects with either a synthetic nanocrystalline hydroxyapatite (Ostim) or a bovine-derived xenogenic bone mineral (BioOss), and covered with a collagen membrane (Bio-Gide). Within the limits of the present case series they concluded that at 12 months after surgery both therapies resulted in clinically important PD reductions and CAL gains.

Oral Maxillofac Res 2016; 9 (3): e15

¹³Roos-Jansåker A-M, Renvert H, Lindahl C, Renvert S. Surgical treatment of peri-implantitis using a bone substitute with or without a resorbable membrane: A prospective cohort study. J Clin Periodontol 2007;34:625–632.

¹⁴Roos-Jansåker A-M, Lindahl C, Persson GR, Renvert S. Long-term stability of surgical bone regenerative procedures of peri-implantitis lesions in a prospective case-control study over 3 years. J Clin Periodontol 2011;38:590–597.

¹⁵ Healing of intrabony peri-implantitis defects following application of a nanocrystalline hydroxyapatite (Ostim) or a bovine-derived xenograft (Bio-Oss) in combination with a collagen membrane (Bio-Gide). A case series. Schwarz F, Bieling K, Latz T, Nuesry E, Becker J J Clin Periodontol. 2006 Jul;33(7):491-9.

CONFIDENTIAL AND PROPRIETARY INFORMATION OF Creighton University School of Dentistry Department of Periodontics

Protocol Number: CUSD2

Revision: October 22nd 2018

Original Issue Date: January 6th 2017

Due to scarcity of literature on the use of alloplast on peri-implant treatment, the purpose of the study is to assess the effectiveness of the novel in-situ hardening β -TCP material, Easy-Graft[®] CLASSIC and polylactide based biodegradable membrane, GUIDOR[®] Biodegradable Matrix Barrier, following clinically adequate decontamination procedures. The author thinks that the specific properties of this grafting material may favor treatment of peri-implantitis. A recent study by Canullo¹⁶ et al. analyzed the efficacy of Easy-Graft[®] CLASSIC on the treatment of peri-implantitis. After removal of granulomatous tissue and decontamination of the titanium exposed implant surface, Easy-Graft was placed on the defect as a protection from soft tissue invasion. The authors noted a pronounced increase in mucosal recession and clinical attachment level with stable peri-implant conditions at six and 12 months. Plaque index, bleeding on probing and probing depths values were significantly reduced at six and 12 months. Radiographic analysis demonstrated from partial to complete filling of the defect in all of the cases at six and 12 months.

Easy-graft remains moldable until it comes in contact with blood or tissue fluids. When the material is soaked in blood in bone defects it hardens in a few minutes to form stable porous scaffold for bone regeneration. This characteristic of graft material gives better handling for the clinician. The hardening of the material could provide an increased stability of the blood clot around implant defect and favor hard tissue deposition and maturation. The Easy-Graft[®] CLASSIC manufacturer recommends GUIDOR[®] Bioabsorbable Membrane Matrix to be used

¹⁶ Canullo I, Peñarrocha Oltra D, Tallarico M, Aloy Prosper A, Chocer H, Peñarrocha Diago M. Surgical treatment of circumferential and semicircumferential defects due to periimplantitis: a prospective case series cohort study. J Oral Science Rehabilitation. 2016 Dec;2(4).

simultaneously in order to maximize its effects. The main difference between this proposed study and Canullo's will be the use of GUIDOR® Bioabsorbable Membrane Matrix in conjunction with Easy-Graft® CLASSIC

The authors of this present study considered the outcome of the peri-implant surgical therapy successful if: implant survival with no peri-implant probing depths (PD) \geq 5 mm, with concomitant bleeding on probing (BOP) and no suppuration, in addition to no additional or progressive bone loss. If these criteria were met, it can be assumed that no further intervention other than nonsurgical maintenance care would be required, and the treatment outcome would therefore be regarded as successful.

2.0 SUMMARY AND STUDY RATIONALE

The present study was designed to demonstrate the EFFICACY OF EASY GRAFT CLASSIC FOR THE TREATMENT OF PERI-IMPLANTITIS.

Easy-graft® CLASSIC, is commercially available alloplastic bone graft granules consists of pure β -TCP, which has been commonly used for the indication of ridge preservation^{17, 18}, peri-implant bone augmentation¹⁹, sinus elevation²⁰ and other treatment of intraoral / maxillofacial osseous defects²¹. It has unique handling capacity based on an extremely thin coating of the graft granules with poly(lactic-co-glycolic acid) (PLGA). PLGA is used as a raw material to manufacture dental membranes, suture materials and resorbable screws. Before application, the granules are mixed with BioLinker® which consists of water and N-Methyl-2-pyrrolidone (NMP). It is non-volatile solvent which has been used in various medical products for more than 10 years. Easy-graft remains moldable until it comes in contact with blood or tissue fluids. When the material is soaked in blood in bone defects it hardens in a few minutes to form stable porous scaffold for bone regeneration. This characteristic of graft material gives better handling for the clinician.

Regenerative treatment of peri-implantitis lesions can be performed in cases with considerable pocket formation and bone loss after the acute infection has been resolved and proper oral hygiene has been instituted. Reported clinical studies indicate that

¹⁷ Leventis MD, et.al. (2016) Minimally invasive alveolar ridge preservation utilizing an in situ hardening β -tricalcium phosphate bone substitute. A multicenter case series. Int J Dent. ID 5406736

¹⁸ Schneider D, et.al. (2014) Labial soft tissue volume evaluation of different techniques for ridge preservation after tooth extraction: a randomized controlled clinical trial. J Clin Periodontol. 41(6): 612-617.

¹⁹ El Sayed et. al. (2015) After socket preservation of upper anterior teeth. Alexandria Dental Journal. 40: 79-85

²⁰ Troedhan A, et.al. (2015) Biomechanical Stability of Dental Implants in Augmented Maxillary Sites: Results of a Randomized Clinical Study with Four Different Biomaterials and PRF and a Biological View on Guided Bone Regeneration. BioMed Res Int. ID 850340

²¹ Neumeyer S. et al. (2010) The use of polylactide-coated β -TCP: Closure of oro-antral communications. Implants. 4:32-36

considerable bone regeneration and re-osseointegration can be obtained by using various types of bone graft materials and membranes. Meta-analysis of latest systematic literature review²² revealed that the weighted mean of marginal bone level change was 1.97 mm, PD reduction was 2.78 mm and BOP reduced by 52.5% by treatment with regenerative treatment. However, a different compatibility between bone grafting material and chemically and mechanically decontaminated implant surface might bring a different clinical outcome. The purpose of the study is to assess the effectiveness of in-situ hardening β - TCP material, easy-graft CLASSIC, for the regenerative treatment of peri-implantitis with polylactide based biodegradable membrane (GUIDOR® Bio-resorbable Matrix Membrane) following clinically adequate decontamination procedures.

The day of surgery will be designated as Day 0. Subjects will have periodontal surgery based on the protocol of Guided Bone Regeneration. Subjects will have a guided bone regeneration surgery with GUIDOR® Bio-resorbable Matrix Membrane and Easy graft classic for the implants experiencing peri-implantitis. The surgical side will be assessed for osseous and implant surface anomalies. Intraoperative and postoperative measurements will be made and the flap will be closed with sutures.

²² Daugela P, et al. (2016) Surgical regenerative treatment for peri-implantitis: Meta-analysis of recent findings in a systematic literature review. J Oral Maxillofac Res. 9 (3): e15

The preliminary phase of the study will comprise completion of medical and dental histories, signing of consent forms, obtaining radiographs and photographs, performing screening assessments to confirm eligibility, and instruction in oral hygiene techniques. Before the periodontal surgical procedure, subjects may undergo plaque removal, then root planing and scaling to the areas to be treated, if such treatment is indicated. The final esthetic outcome of the treated sites will be evaluated by the patients using the Visual Analog Scale (VAS) ranging from "Very Unsatisfied" to "Very Satisfied" (before and after viewing baseline photos). Other clinical assessments will include: subject pain/discomfort questionnaire, change in probing depth, change in clinical attachment level, change in width of keratinized tissue from baseline to 6 and 12 months and change in radiographic bone gain and pathology. Digital photographs will be obtained at each study visit and radiographs of the test sites will be made at the baseline, 6 and 12 month visits.

The primary efficacy parameters will include:

- Esthetic satisfaction from baseline to six months of all treated areas, as assessed by both the examiner and the subject using the Visual Analog Scale (VAS), prior to and after viewing baseline photos
- Subject pain/discomfort questionnaire
- Change from baseline in probing depth (PD) measured from the mucosal margin to the bottom of the probeable pocket

- Gingival recession (Rec) measured from the implant platform (IP) to the mucosal margin
- Change from baseline visit in clinical attachment level (CAL) measured from IP to the bottom of the probeable pocket
- Change from baseline in width of the keratinized tissue (KT)
- Change from baseline in radiographic a) bone gain; b) pathology

INVESTIGATIONAL DEVICE

GUIDOR® easy-graft® CLASSIC

GUIDOR® easy-graft® CLASSIC is bone grafting system contains: syringe containing betatricalcium phosphate (β -TCP) granules coated with poly (lactide-co-glycolide) (PLGA) and ampule containing BioLinker® Activator (N-methyl-2-pyrrolidone and water).

Easy-graft CLASSIC is a bio-resorbable, synthetic, porous bone graft substitute. It consists of two components: granules (supplied in syringe) and BioLinker activator (supplied in ampule). After mixing the components together, easy-graft CLASSIC forms a moldable mass that can be applied directly from the syringe into the bone defect. Easy-graft CLASSIC hardens in contact with body fluids, allowing a working time of approximately one minute after application into the bone defect. Easy-graft CLASSIC is provided in the particle size of 500 – 1000 μ m. The scaffold is a biocompatible and osteoconductive that allows for complete resorption by the

body. β -TCP and PLGA are derived from synthetic raw materials. Easy-graft CLASSIC comes sterilized via gamma irradiation.

GUIDOR® Bio-resorbable Matrix Barrier

GUIDOR® Matrix Barrier are made of polylactic acid with a citric acid ester. It is double-layered; the external layer has large rectangular perforations which face the overlying soft tissues and permit connective tissue infiltration, while the inner layer has small circular perforations which face bone and inhibit fibrous tissue ingrowth. It maintains its barrier function for 6 weeks at least, with complete resorption occurring by 6 months. Available membrane dimensions are 15 mm x 20 mm or 20 mm x 28 mm. The membrane is provided in a transparent plastic tray in a sealed aluminum pouch. It comes sterilized via e-beam.

3.0 STUDY DESIGN

3.1 Overall Study Design

This study will be case series, with two periodontists and an examiner. Both of the periodontists will perform surgical procedures and record surgical measurements. The blinded examiner will perform all other clinical assessments. 15 subjects will be enrolled. Written informed consent will be obtained from each subject prior to any study related procedures.

The study will follow subjects for safety and efficacy for 6 and 12 months after their surgical treatment.

Screening will take place no more than 32 days prior to the first treatment and will include the clinical assessments required to confirm eligibility. Clinical photograph, radiographs of the implant treated, clinical measurements will be taken and recorded (Pocked Depth, Mucosal Recession, Clinical Attachment Level). Two to four (2-4) weeks prior to the first study treatment, subjects may undergo plaque removal and root planing and scaling to the areas to be treated, if appropriate. Also, they will receive personalized oral hygiene instructions to reach full-mouth plaque score (FMPS) <20% and full-mouth bleeding score (FMBS) <20%, which will be considered requirement for surgery to occur.

The day of surgery will be designated as Day 0. Subjects will have peri-implant regeneration surgery.

If possible, implant crown will be removed with attention not to damage it. Healing screw will be placed on the implants. Upon flap elevation and debridement of the peri implant lesion, the operator will record the type of bony defect associated to the treated implant (see Inclusion criteria 3). Titanium Implant surface will be debrided with rotating burs and brushes (PERI-SET Swden&Martina Inc.), and decontaminated with EDTA gel (Straumann® PrefGel. pH neutral, 24% EDTA) for 2 minutes and with the alternation of Perio-Flow Chlorhexidine mouthwash (GUM® ParoEx®, Chlorhexidine Gluconate Oral Rinse USP 0,12%, SUNSTAR) saline water and H₂O₂ using cotton pellets. After the completion of these procedures, Easy-graft® CLASSIC will be placed to fill the peri-implant defect.

GUIDOR® Bio-resorbable Matrix Membrane will be placed on top of the easy-graft classic. If the implant crown was successfully removed and healing screw placed, the implant will be covered by the flap and submerged. Intraoperative and postoperative measurements will be made and the flap will be closed with sutures. Patients will be instructed to take 500 mg of amoxicillin three times a day for 7 days, starting at least one hour prior the procedure. Fifteen (15) male or female subjects, aged 21 to 85 years, will be recruited for the study from existing patient databases, as well as, from screenings of volunteers responding to advertisements, if necessary.

Objectives

The objectives of this study are to assess the EFFICACY OF EASY GRAFT CLASSIC FOR THE TREATMENT OF PERI-IMPLANTITIS.

3.2.1 Primary Efficacy Endpoints

- Change from baseline in probing depth
- Change from baseline in clinical attachment level
- Change from baseline in width of the keratinized tissue
- Change from baseline in radiographic a) bone gain; b) pathology
- Esthetic satisfaction from baseline to six months of all treated areas, as assessed by both the examiner and the subject using the Visual Analog Scale (VAS), prior to and after viewing baseline photos

- Subject pain/discomfort questionnaire

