3.5 Clinical Assessments

3.5.1 Summary of Clinical Assessments

All examinations and measurements will be performed in accordance with the Schedule of Events.

Data will be collected and assessments will be made on study sites treated.

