3.5.2 Primary Efficacy Assessment

- Esthetic satisfaction from baseline to 6 and 12 months of all treated areas, as assessed by both the examiner and the subject using the Visual Analog Scale (VAS), prior to and after viewing baseline photos
- Subject pain/discomfort questionnaire

- Change from baseline in probing depth
- Change from baseline visit in clinical attachment level
- Change from baseline visit in width of the keratinized tissue
- Change from baseline in radiographic a) bone gain; B) pathology

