3.6 Schedule of Investigational Events

3.6.1 Screening Visit (Visit 1)

At the screening visit the following procedures and assessments will be performed within 32 days prior to surgery:

- Informed Consent
- Subject registration
- Medical history collection and physical examination:
 - Record of past therapy
 - Urine pregnancy test (females of child-bearing potential only)
 - Medications
- Dental history collection
 - Record of past therapy
- Screening assessments to determine eligibility:
 - O'Leary Plaque Index
 - Probing depths
 - Implant mobility,
 - Clinical attachment level
 - Obtain baseline radiographs of study sites
- Dental cleaning

- Oral hygiene instruction
- Supragingival plaque control, as appropriate
- Examiner and subject baseline esthetic satisfaction VAS assessments
- Radiographs of all target study sites

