3.6.2 Baseline/Treatment (Visit 2)

Visit 2 may occur concurrently with Visit 1. If separate visits are to occur, Visit 2 must occur within 32 days of the screening examine.

- Examiner calibration (for first 2 subjects enrolled only)
- Preoperative and Intraoperative digital photographs
- Concomitant medications
- Surgical procedure
- Post-operative instructions
- Collection of any Adverse Events

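### Change from baseline in keratinized tissue width is a primary endpoint, but no reading is scheduled before surgery, so the change cannot be computed

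*Combined protocol and SAP*

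**What the plan says.** Section 3.2.1 lists six primary efficacy endpoints, one of which is "Change from baseline in width of the keratinized tissue". Section 3.5.2 repeats it as "Change from baseline visit in width of the keratinized tissue". Section 2.0 gives the interval: "change in width of keratinized tissue from baseline to 6 and 12 months". The synopsis places the same item under "Stability and health of the attachment apparatus at 6 and 12 months by measuring".

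Timing is left to the schedule. Section 3.5.1 states: "All examinations and measurements will be performed in accordance with the Schedule of Events". The opening of 3.7 (Summary of Clinical Assessments) says the same and points to the flowchart. The KT entry in 3.7 explains how to measure (by probe, from the free gingival margin to the muco-gingival junction, to 0.5 mm) but names no visit.

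For the period before surgery, 3.1 says of screening that "clinical measurements will be taken and recorded (Pocked Depth, Mucosal Recession, Clinical Attachment Level", and 3.4.2 repeats this. KT is not among the three measurements. The Visit 1 list (3.6.1) has plaque index, probing depths, mobility, attachment level, esthetic ratings and an instruction to "Obtain baseline radiographs of study sites". The Visit 2 list (3.6.2), although headed as baseline, has examiner calibration, "Preoperative and Intraoperative digital photographs", medications, the operation, instructions and adverse events. KT is in neither list.

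**The concern.** A change from baseline needs a reading before treatment and one after it. This is a single-arm case series, so each implant's own pre-operative value is the only comparator. If KT width is not recorded before the flap is raised, it cannot be measured later, because the tissue has been altered.

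The likely makeshift is to treat the Week 1 value as baseline. That value already contains the effect of the flap surgery, so the change would run from one post-operative state to another and would not answer the question the endpoint asks.

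**Working it through.** The documents give no figure to reproduce here, so the check is a count of scheduled KT readings.

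**Inputs.** At most 15 subjects and 20 implants (synopsis). Endpoint time points: 6 and 12 months (synopsis and section 2.0). Surgery: Visit 2, Day 0 (3.2.3).

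| Where a KT reading could appear | Before surgery | After surgery |
|---|---|---|
| Screening narrative (3.1, 3.4.2) | 0 | not applicable |
| Visit 1 list (3.6.1) | 0 | not applicable |
| Visit 2 list (3.6.2) | 0 | not applicable |
| Defect examination during surgery (3.7) | 0 | not applicable |
| Visit lists 3.6.3 to 3.6.7 | not applicable | 4 (Visits 3, 5, 6, 7) |
| Flowchart row | 0 | 4 (Visits 4 to 7) |

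**Flowchart header.** The time labels are shifted against the visit numbers, possibly through text extraction, and I do not count this as an error. Read by visit number, the KT marks are at Visits 4 to 7. Read by time label, they are at Day 7, Month 1, Month 3 and Month 6. All are after surgery on either reading. Two other rows fit the visit numbers: second-stage surgery at Visit 6 (6 months in 3.4.2) and radiographs at Visits 6 and 7 (6 and 12 months in 3.7.4).

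**Size.**
- Post-operative readings: 20 implants × 4 = up to 80.
- Change values wanted: 20 implants × 2 time points = up to 40.
- Baselines available: 0. Computable change values: 0 of up to 40.

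**Can the baseline come from elsewhere?** Recession and attachment level locate the soft-tissue margin and the base of the pocket, not the muco-gingival junction, so KT width cannot be derived from them. The pre-operative photographs are not the probe measurement that 3.7 defines, and no scale is specified for them. The intraoperative and postoperative measurements mentioned in 3.1 and 3.4.2 do not name KT and are not pre-operative. The missing-data text in 5.0 provides for discussing individual subjects who lack a baseline. It names no substitute and cannot supply a value that the schedule omits for everyone.

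**A second mismatch.** By visit number, the visit lists put KT at Visit 3 and not Visit 4, while the flowchart has it at Visit 4 and not Visit 3. If the time labels were right instead, the two would disagree at Months 1 and 12.

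**Comparison with PD and CAL.** Probing depth and attachment level each have a pre-surgical reading at Visit 1 in both the list and the flowchart, so their changes can be computed. The only loose end is that 3.2.3 and 3.6.2 attach the word baseline to Visit 2, where neither is scheduled.

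**The case against.** The strongest reply is that the visit lists are not exhaustive. Recession is a primary parameter in 2.0 and is due at 6 and 12 months under 3.7, yet it appears in no visit list and no flowchart row. The flowchart also leaves out attachment level at Visits 4 and 5, although 3.6.4 and 3.6.5 list it. An endpoint defined as a change from a baseline visit implies that someone will take a baseline, and a site might do so unprompted. This is fair as far as it goes: the claim concerns the plan as written and cannot say what a site will do. But recession is named in the screening narrative and KT is not, and 3.5.1 makes the schedule govern. Nothing requires the reading.

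A second point is that the counts of 80 and 40 assume KT can be read at every implant and visit. Where the crown is removed, the implant is covered until second-stage surgery at 6 months (3.4.2), and the protocol does not say how the margin is then defined. This stands, and it is why the figures are upper limits. It does not affect the count of 0 before surgery.

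Third, KT is one of six co-listed primary items, the success definition at the end of section 1.0 does not use it, and section 5.0 states no hypothesis test. This limits the damage to one endpoint. It does not make that endpoint computable.

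**Conclusion.** The concern holds and must be fixed. Under the plan as written, one listed primary endpoint cannot be calculated for any implant: 0 scheduled pre-operative KT readings against 4 post-operative ones, and 0 of up to 40 change values. The conclusion rests on two things: that the schedule governs, as 3.5.1 and 3.7 say, and that sites take no unscheduled reading. It does not depend on how the flowchart header is read. The other primary endpoints and the success definition in section 1.0 are unaffected by this gap.

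One related matter is for interpretation only. The Visit 1 probing depth also decides eligibility (3.3.1) and may precede scaling (3.1, 3.4.1), so the observed reduction may include regression to the mean and a response to hygiene treatment. No size in millimetres can be given, because the documents do not say how the six sites around an implant are combined.

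**What to change.** 1. Add to the Visit 1 list in 3.6.1, beside probing depth and attachment level: *Width of keratinized tissue, recorded by the examiner*. Mark it at Visit 1 in the flowchart and add a CRF field. The alternative is Visit 2 in 3.6.2, specified as before incision. Use one visit for all subjects and state: *This reading is the KT baseline.*
2. For any implant already operated on without such a reading, report post-operative KT values only. Do not use Week 1 as baseline.
3. Reconcile the post-operative KT visits in 3.6.3 to 3.6.7 with the flowchart, and check that its time labels match its visit numbers.
4. State that the Visit 1 reading is the baseline for probing depth and attachment level, and report the caution on regression to the mean and hygiene response. If these are also read before incision alongside KT, show the change from that reading as a sensitivity result.

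The cost is one line each in the visit list, flowchart and CRF, and a few minutes of probing per implant. Visit 1 needs no extra appointment. Visit 2 needs the examiner present on the day of surgery. Implants already treated without a reading drop out of the KT change analysis, which may then have fewer than 20.
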